# 1. Analysis Objectives and Endpoints

## 1.1 Primary Objective

To evaluate the effect of Brain Dynamic Audio Stimulation (BDAS) on insomnia severity as measured by the **Insomnia Severity Index (ISI)** before and after a two-week intervention.

## 1.2 Secondary Objectives

To assess the effect of BDAS on objective sleep-related parameters, including:

- Sleep onset success rate
- Sleep onset latency
- Sleep efficiency
- Short-term sleep stage distribution derived from EEG-based hypnograms

## 1.3 Endpoints

### Primary Endpoint

- Mean change in total ISI score from baseline (pre-intervention) to post-intervention (after 2 weeks)

### Secondary Endpoints

- Sleep onset success rate following BDAS exposure
- Mean sleep onset latency (seconds) before and after 2 weeks of BDAS use
- Mean sleep efficiency (%) before and after BDAS intervention
- Proportion of time spent in each sleep stage (Wake, N1, N2, N3, REM) during EEG recording sessions

---

## 2. Analysis Populations

Population	Definition
Full Analysis Set (FAS)	All participants who received at least one BDAS session and provided baseline ISI data
Per-Protocol Set (PPS)	Participants completing $\geq 80\%$ of BDAS sessions without major protocol deviations
Safety Set	All participants who initiated BDAS intervention

- Primary analyses will be conducted on the **FAS**
- Sensitivity analyses will be performed using the **PPS**

---

## 3. General Statistical Principles

- All statistical analyses will be conducted using **SPSS (v28 or later)** or **R (v4.3 or later)**
- All tests will be **two-tailed**
- Statistical significance will be defined as **p < 0.05**
- Continuous variables will be summarized as:
  - Mean  $\pm$  standard deviation (SD), or
  - Median and interquartile range (IQR) if non-normally distributed
- Categorical variables will be summarized as counts and percentages
- Normality will be assessed using **Shapiro–Wilk tests** and visual inspection (Q–Q plots)

---

## 4. Handling of Missing Data

- For ISI analysis, participants with both baseline and post-intervention data will be included
- No imputation will be performed for missing objective sleep measures
- Sensitivity analyses excluding incomplete cases will be conducted to assess robustness

---

## 5. Statistical Methods

### 5.1 Primary Analysis: ISI Score

- **Paired-sample t-test** will be used to compare pre- and post-intervention ISI scores
- If normality assumptions are violated, the **Wilcoxon signed-rank test** will be applied
- Effect sizes will be reported using:
  - **Cohen's d**
  - **Hedges' g**
- Mean difference with **95% confidence intervals (CI)** will be presented

---

### 5.2 Secondary Analysis: Sleep Onset Success Rate

- Sleep onset success will be defined as transition from wakefulness to any sleep stage during the recording period
- Success rates will be summarized descriptively as proportions (%)
- No inferential testing is planned due to the exploratory nature of this endpoint

---

### 5.3 Secondary Analysis: Sleep Onset Latency

- Sleep onset latency is defined as time (seconds) from recording start to first epoch of sleep
- **Independent-sample t-tests** will be used to compare latency between:
  - Initial use
  - After 2 weeks of BDAS use
- Each sleep session will be treated as an **independent observation** to maximize statistical power
- Effect sizes will be reported using Cohen's d and Hedges' g

---

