## 5.5 Exploratory Analysis: Sleep Stage Distribution

- Sleep stages will be classified according to **AASM criteria**
- Proportion of time spent in each stage (Wake, N1, N2, N3, REM) will be summarized descriptively
- Where appropriate, paired-sample t-tests or Wilcoxon tests will be applied for exploratory comparisons
- Results will be interpreted descriptively due to short recording duration

---

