## 8. Interim and Sensitivity Analyses

- No interim analyses are planned
- Sensitivity analyses will include:
  - Reanalysis excluding identified outliers
  - Non-parametric alternatives where appropriate
  - PPS-based comparisons

---

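### SAP 5.3 has no rule for sessions without sleep onset; dropping them makes mean latency conditional on falling asleep and distorts the comparison when the success rate changes

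*SAP*

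**What the plan says.** The SAP lists as a secondary endpoint "Mean sleep onset latency (seconds) before and after 2 weeks of BDAS use". Section 5.3 defines the measure: "Sleep onset latency is defined as time (seconds) from recording start to first epoch of sleep". It compares initial use with two weeks by an independent-sample t-test, taking each session as one observation.

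Section 5.2 makes falling asleep a separate yes/no endpoint: "Sleep onset success will be defined as transition from wakefulness to any sleep stage during the recording period". That endpoint is descriptive only: "No inferential testing is planned due to the exploratory nature of this endpoint". Section 5.5 adds, of the sleep-stage data, "Results will be interpreted descriptively due to short recording duration".

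For missing data, section 4 states: "No imputation will be performed for missing objective sleep measures". The related sensitivity analysis is "Sensitivity analyses excluding incomplete cases will be conducted to assess robustness", and section 8 adds "Non-parametric alternatives where appropriate".

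None of these passages gives a session without sleep onset a latency value, a rank or a censoring time. Neither do the analysis populations (SAP 2), the general principles (SAP 3), the usable-recording rule (SAP 6) or Protocol sections 6 and 7.

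**The concern.** A success rate is worth reporting only if some sessions may fail, and short recordings make failures plausible. Such a session has no first sleep epoch and so no latency under 5.3. A t-test needs a number for each session and section 4 forbids filling one in, so the natural reading is that these sessions drop out.

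They are not uninformative. A session without onset tells us that latency exceeds the recording time; it is right-censored. Dropping it selects sessions on the outcome under test. Onset success is itself expected to respond to the intervention, so the selection may differ between initial use and two weeks.

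If success rises, the latency test can understate the improvement or occasionally reverse it. If success falls, it can hide a worsening or show a false benefit. Because success is not tested, latency is the only planned inferential test aimed at sleep onset, and it would leave out the failures. Sleep efficiency (SAP 5.4) is 0%, and so defined, for those same sessions. The two tested objective endpoints would then rest on different sets of sessions.

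**Working it through.** **Inputs.** The documents give no latency, success rate or recording length. The only sample-size figure, 15 participants, is for ISI, so there is no plan figure for latency to reproduce. Assumed here: recording length T = 30 min, borrowed from the session length in Protocol section 3, with 15 and 45 min as a range; and five pairs of success rates.

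**Identity.** Let s be the success rate and m the mean latency among sessions with onset. The restricted mean, with non-onset counted as T, is R = s·m + (1−s)·T. From time 0 to time 1:

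R₁ − R₀ = s₁(m₁ − m₀) − (s₁ − s₀)(T − m₀).

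The planned test sees only m₁ − m₀. The second term, the gain or loss from a change in success, is invisible to it. If s does not change, the second term is zero and both measures have the same sign.

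**Assumption A: constant onset hazard.** λ = −ln(1−s)/T; m = 1/λ − T·e^(−λT)/(1 − e^(−λT)); R = (1 − e^(−λT))/λ. Share lost = 1 − (change in m)/(change in R). At T = 30 min:

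| Success | m (min) | R (min) | Share lost |
|---|---|---|---|
| 60→70% | 12.74→12.06 | 19.64→17.44 | 69% |
| 60→90% | 12.74→9.70 | 19.64→11.73 | 62% |
| 80→95% | 11.14→8.44 | 14.91→9.51 | 50% |
| 90→98% | 9.70→7.06 | 11.73→7.52 | 37% |
| 95→99% | 8.44→6.21 | 9.51→6.45 | 27% |

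Check of the identity for 60→90%: 0.9 × (−3.04) − 0.3 × (30 − 12.74) = −2.74 − 5.18 = −7.92, which matches the table.

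The share lost does not depend on T, but the minutes scale with it. For 60→90%, onset-only against restricted change is −1.5 vs −4.0 (15 min), −3.0 vs −7.9 (30 min) and −4.6 vs −11.9 (45 min).

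**Assumption B: lognormal latency, log-SD σ.** μ = ln T − σΦ⁻¹(s); E = exp(μ + σ²/2)·Φ((ln T − μ − σ²)/σ); m = E/s; R = E + T(1−s). Share lost for the same five pairs:

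- σ = 0.5: 39, 36, 30, 22, 15%
- σ = 1.0: 47, 44, 38, 29, 22%

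The sign did not reverse in any A or B case.

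**When the sign can reverse.** Suppose 9 of 15 sessions reach sleep at 10 min before. After two weeks the same 9 do so at x min and 4 more at c min. The onset-only mean rises if (9x + 4c)/13 > 10, that is, c > (130 − 9x)/4: c > 10 for x = 10, 14.5 for x = 8, 16.75 for x = 7. With T = 30 min:

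- x = 10, c = 25: onset-only 10.0 → (9×10 + 4×25)/13 = 14.6. Restricted (9×10 + 6×30)/15 = 18.0 → (9×10 + 4×25 + 2×30)/15 = 16.7. An improvement looks like a worsening.
- x = 7, c = 15: onset-only 10.0 → (9×7 + 4×15)/13 = 9.5. Restricted 18.0 → (9×7 + 4×15 + 2×30)/15 = 12.2. A gain of 5.8 min shows as about 0.5 min.
- The first case run backwards (success falls): onset-only 14.6 → 10.0, apparently 4.6 min better; restricted 16.7 → 18.0, in fact 1.3 min worse.

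**The case against.** The strongest reply is that exclusion is inferred. The SAP never writes it, and if a non-onset session is censored rather than missing, the no-imputation rule arguably does not govern it. An analyst could then enter the recording length without breaching the plan. That is right as far as it goes, but it leaves the choice open after the data are seen, and the text still has to be completed.

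Second, mean latency among sessions that reach sleep is a legitimate quantity, reported beside a success rate; it is biased only relative to a mean over all sessions. This stands as a point about the target, and the reference here is the restricted mean. It does not rescue a before-after test of the onset-only mean as evidence on time to fall asleep, since the two groups of sessions are selected differently.

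Third, there is partial mitigation. The success rate, sleep efficiency and the proportion of time awake would all show failures to sleep. Rank tests are allowed among the sensitivity analyses, but no rank is assigned to non-onset. A reader would see part of the problem; the latency test itself would not be repaired.

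Finally, the frequency of non-onset is unknown, reversal needs late converters, and this is a secondary endpoint in an exploratory single-group study of 15. All of that stands and limits the severity. It does not remove the gap, because 5.3 plans a significance test with effect sizes.

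**Conclusion.** The concern holds. Taken together, the definition in 5.3, the t-test and the no-imputation rule in section 4 lead to dropping sessions without onset. The resulting comparison is distorted, relative to restricted mean latency over all sessions, whenever the success rate differs between initial use and two weeks.

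The size cannot be fixed from the documents. Over the success rates tried, the loss is 27% to 69% of the restricted-mean change under a constant hazard and 15% to 47% under lognormal latencies. A reversed sign is possible but was seen only in constructed examples with late converters. If every session reaches onset there is no problem.

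Confidence is high that the rule is absent; that exclusion would be the practice is an inference. The change should be made, but it bears on one secondary endpoint and leaves the primary ISI result untouched.

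**What to change.** In SAP 5.3:

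1. State the recording length, or a common truncation time for all sessions.
2. State that a session without sleep onset is kept as right-censored at that time and does not count as missing under section 4.
3. Compare restricted mean latency (non-onset = truncation time), or use a time-to-event analysis or a rank analysis with non-onset ranked worst. Whichever is chosen should allow for repeated sessions within a participant, for example one mean restricted latency per participant and time point, compared within participant. The treatment of sessions as independent is a separate matter; the non-onset rule is needed whichever test is used.
4. Report onset-only mean latency beside the success rate as a descriptive supplement.

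The cost is SAP wording and slightly more analysis, using only the recordings and their durations. The downside is that the mean becomes a capped one whose value depends on the truncation time, so that time should be set before the data are examined.

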### 5.4 Secondary Analysis: Sleep Efficiency

- Sleep efficiency is defined as: **(Total sleep time / total recording time) × 100%**
- Independent-sample t-tests will be used to compare sleep efficiency before and after BDAS intervention
- Effect sizes (Cohen's d, Hedges' g) and 95% CIs will be reported

---

## 5.5 Exploratory Analysis: Sleep Stage Distribution

- Sleep stages will be classified according to **AASM criteria**
- Proportion of time spent in each stage (Wake, N1, N2, N3, REM) will be summarized descriptively
- Where appropriate, paired-sample t-tests or Wilcoxon tests will be applied for exploratory comparisons
- Results will be interpreted descriptively due to short recording duration

---

## 6. Outlier and Data Quality Management

- Outliers ( $>3$  SD from the mean) will be reviewed against raw EEG and recording logs
- Artifactual recordings (movement, muscle noise) will be excluded prior to analysis
- A minimum of **80% usable recording time** is required for inclusion in EEG-based analyses

---

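### Excluding whole recordings for movement or muscle noise can selectively lose failed sleep attempts, and no planned analysis shows what that does to sleep onset success or sleep efficiency.

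*SAP*

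**What the plan says.** SAP Section 6 has two bullets on recording quality. One says "Artifactual recordings (movement, muscle noise) will be excluded prior to analysis". The other says "A minimum of 80% usable recording time is required for inclusion in EEG-based analyses". The first acts on recordings, not epochs, and does not say how much artifact makes a recording artifactual. Neither bullet says that the decision is made without regard to time point, and the SAP does not say whether the 80% figure is the threshold for the first bullet.

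The endpoints affected are defined in SAP Sections 5.2 and 5.4. Onset success is a "transition from wakefulness to any sleep stage during the recording period", so a recording with no sleep is a failure. Success is descriptive only: "No inferential testing is planned due to the exploratory nature of this endpoint". Efficiency is sleep time as a percentage of recording time, so a recording with no sleep scores 0. Efficiency is tested: "Independent-sample t-tests will be used to compare sleep efficiency before and after BDAS intervention".

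Protocol Section 6 lists EMG among the signals used to separate Wake from the sleep stages. SAP Section 4 imputes nothing for objective measures, and its sensitivity analysis removes further cases. SAP Section 8 adds outlier removal, non-parametric tests and the per-protocol set.

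**The concern.** Movement and muscle activity plausibly go with lying awake, and being awake is what these endpoints measure. A rule that deletes a recording for movement may therefore select on the outcome. A participant who fails to fall asleep and moves a good deal contributes neither a failure to the success rate nor a zero to mean efficiency. What remains is weighted towards recordings with sleep.

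Two things are at stake. The levels of success and efficiency could be reported too high. And if restlessness, or the strictness of the exclusion decision, differs between first use and week 2, the exclusion alone could create or hide a before-after difference in efficiency. The planned analyses would not reveal either.

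**Working it through.** **Plan's own figure.** The documents give no artifact rate, exclusion rate, success rate or mean efficiency, so there is nothing to reproduce here. The sample-size statement in SAP Section 7 concerns the ISI and does not bear on this point. Every rate below is an assumption.

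**1. Formula for success.** Let p be the true success rate, and k1 and k0 the shares of sleep and no-sleep recordings that are kept.

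Observed success = p·k1 / [p·k1 + (1 − p)·k0]

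If k1 = k0, the observed rate equals p and there is no bias.

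**2. Range over assumed losses, p = 70%.** With 5% of sleep recordings lost, p·k1 = 0.70 × 0.95 = 0.665.

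| No-sleep recordings lost | Calculation | Observed |
|---|---|---|
| 20% | 0.665 / (0.665 + 0.240) | 73.5% |
| 40% | 0.665 / (0.665 + 0.180) | 78.7% |
| 60% | 0.665 / (0.665 + 0.120) | 84.7% |

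Over true rates of 50% to 85%, the same losses give a bias of +2.1 to +20.4 points. If sleep recordings were the ones lost more often (20% against 5%), the result is 0.560 / (0.560 + 0.285) = 66.3%, a bias of −3.7 points.

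**3. The 80% rule alone.** This simulation assumes 60 epochs per recording, 3% artifact in sleep, and a log-normal wake artifact rate (log-SD 0.6) with mean 10%, 15% or 25%. Recordings with more than 20% artifact are dropped. Half of the recordings have no sleep and the rest average 50% efficiency, so true mean efficiency is 0.5 × 0 + 0.5 × 50 = 25%.

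- At 25% wake artifact, 49-50% of no-sleep recordings are kept against 80-82% of those with sleep. With k1 = 0.80 and k0 = 0.49, a true 50% reads as 0.400 / (0.400 + 0.245) = 62%. A true 80% reads as 0.640 / (0.640 + 0.098) = 87%.
- At 15%, a true 50% reads as about 55%.
- At 10%, a true 50% reads as 52% and a true 80% as 81%.
- Across 10-25%, a true mean efficiency of 25% reads as 26-35%. At 25% wake artifact the range is 31-35%, depending on how efficiency is spread among recordings with sleep.

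**4. Before-after efficiency with no true change.** Take true efficiency with mean 50% and SD 25 points, and probability of exclusion = 0.05 + slope × wake fraction. Slopes 0, 0.2, 0.4 and 0.6 give observed means of 50.0%, 51.5%, 53.4% and 55.8%.

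- Equal slopes in both periods: shift 0, type I error about 5%.
- Slopes 0.2 and 0.6: shift 55.8 − 51.5 = 4.3 points. Type I error is 6.6% at 15 recordings per period, 10.9% at 50 and 17.8% at 105 (counts assumed). Exchanging the periods reverses the sign.

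**5. Efficiency denominator.** In a recording with 80% usable time and true efficiency 70%, suppose artifact is unrelated to stage, stays in the denominator and is not scored as sleep. The result is 0.8 × 70 = 56%. If all the artifact falls in wake and is removed from the denominator, the result is 70 / 0.8 = 87.5%. The SAP does not say which treatment applies.

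**The case against.** The strongest objection is that the key premise is assumed. Nothing in the documents says artifact is commoner in wake, and since EMG is a staging input, muscle activity need not make an epoch unusable. Step 2 shows that the bias reverses if sleep recordings are lost more often. This stands: the direction is plausible, not established.

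Secondly, the figures in step 3 come from the 80% rule alone, which the fix retains. This also stands. The bias therefore does not depend on a strict reading of the artifact bullet, but epoch-level rejection by itself would not remove it.

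Thirdly, the effect is small where success is high or wake artifact is low, and the endpoints are secondary or exploratory. Both are true and limit the weight of the point.

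A reader might infer more than the documents support:

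- **That the two bullets in Section 6 contradict each other.** The 80% bullet may simply be the threshold for the artifact bullet. This is an ambiguity.
- **That each excluded recording breaks a pair.** Efficiency and latency are compared with independent-sample tests (SAP 5.3 and 5.4). Pairing appears only in the exploratory stage comparisons of SAP 5.5.
- **That the rule is what makes latencies undefined.** A recording with no sleep has no first sleep epoch, so it has no latency whether or not it is excluded.

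**Conclusion.** The concern holds as a risk. Whole-recording exclusion can select on wakefulness, its threshold is unclear, and no planned analysis restores or bounds what is excluded. Under the assumptions in step 3, overstatement ranges from about 1 or 2 points to 12 points for success (80% read as 81% at the low end, 50% read as 62% at the high end) and from 1 to 10 points for a true mean efficiency of 25%.

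It would go too far to say that the rule removes the wakeful recordings, or that success and efficiency are overstated; without artifact rates by state, neither can be shown. Nor is the before-after contrast necessarily biased. With no true change, an equal exclusion mechanism in both periods leaves it at zero, and an unequal one can move it either way. The inferential risk falls on efficiency, since success is not tested. The primary ISI analysis does not use these recordings and is unaffected. The point warrants a change to the SAP but does not threaten the main result.

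**What to change.** Amend SAP Section 6 as follows.

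(a) Reject artifact at epoch level and make the 80% rule the only recording-level exclusion. State whether unusable time stays in the efficiency denominator.

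(b) Decide exclusions before outcomes are computed and without regard to period. Tabulate them, with reasons, by period.

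(c) Because (a) alone does not remove the selection, add a sensitivity analysis that keeps every attempted recording and counts excluded ones as no onset and efficiency 0. Report it beside the main result and label it a worst-case bound, since it misclassifies anyone who slept but whose recording failed. In the 25% wake-artifact example, the main result is 62% and the bound is 0.5 × 0.80 = 40%, so the two bracket the true 50%. It bounds the level in each period, not the difference between periods; for the contrast, read it with the table in (b).

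The cost is SAP wording and one extra table, with no new data. The small downside is that reported success and efficiency may look less favourable.

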## 7. Sample Size Considerations

- This study is exploratory in nature
- Based on prior observations of ISI improvement (mean reduction  $\approx 5$  points, SD  $\approx 4$ ), a sample size of **15 participants** provides sufficient power to detect large within-subject effects
- No formal hypothesis-driven power calculation is applied for secondary outcomes

---

## 8. Interim and Sensitivity Analyses

- No interim analyses are planned
- Sensitivity analyses will include:
  - Reanalysis excluding identified outliers
  - Non-parametric alternatives where appropriate
  - PPS-based comparisons

---

## 9. Reporting of Results

- Results will be reported as:
  - Mean  $\pm$  SD
  - Mean difference (95% CI)
  - p-values and effect sizes
- Graphical presentations may include:
  - ISI pre-post boxplots
  - Sleep onset latency distributions
  - Sleep efficiency comparison plots
  - Sleep hypnogram examples

---

## 10. Deviations from the Statistical Analysis Plan

Any deviations from this SAP will be:

- Documented with justification
- Approved prior to final database lock
- Clearly described in final reports and publications
